# Introduction

## Purpose

The goal of this study is to evaluate the effectiveness of a brief, intensive 1-day psychotherapy group intervention (Acceptance and Commitment Therapy, ACT), compared to a 12 week time control group on anxiety symptoms, vascular function, inflammation, muscle sympathetic nerve activity (mSNA), and oxidant stress. Individuals who are interested in the study will be identified by an online screening survey and will be contacted by the research team; advertisements, flyers and mass emails will direct individuals to the online screening survey. Those deemed eligible to participate will be randomized to the ACT intervention or the control group. Assessments of anxiety symptoms (via various surveys) and vascular function (via non-invasive, well-established techniques) will be performed at baseline and 12 weeks post-ACT group intervention session. In addition, reassessment of anxiety symptoms via aforementioned surveys will take place 6 weeks post-ACT group session. After 12 weeks, anxiety and vascular assessments will be repeated to re-evaluate severity of anxiety symptoms, vascular function, inflammation, and oxidant stress.

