## Research Question and Hypothesis

We hypothesize that reducing the burden of anxiety symptoms using Acceptance and Commitment Therapy (ACT) will improve vascular function, inflammation, mSNA, and oxidant stress. If our hypothesis is correct, then we predict that: 1) Vascular function, inflammation, muscle sympathetic nerve activity (mSNA), and oxidant stress will be elevated in individuals with anxiety compared to those with low or no anxiety, 2) ACT will improve forearm blood flow during reactive hyperemia; 3) ACT will decrease mSNA; 4) ACT will improve microvascular, including retinal vascular, and large elastic artery function per pulse wave velocity (PWV) measurements and 5) ACT will improve autonomic function measured by 24-hour blood pressure variability and heart rate variability measures. We will also be able to explore other secondary endpoints related to oxidant stress and inflammation in vascular endothelial cells. If anxiety increases inflammation, then we predict that ACT will reduce circulating pro-inflammatory cytokines, and produce a phenotype of endothelial cell proteins reflecting decreased inflammation compared to pre-treatment. And if anxiety increases oxidative stress, then we predict that ACT will produce a phenotype of endothelial cell proteins reflecting decreased oxidant stress and increased nitric oxide synthase activity.

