### Secondary Endpoint Analysis

State and Trait subscales of the STAI will be secondarily modeled as the dependent variable to assess changes in the domains of trait and state anxiety.

The novel physiological variables (vascular function, mSNA, inflammation) will serve as secondary outcomes and will be explored in analogous to the above. We will also assess for any relationship between these variables and changes in anxiety across groups in linear regression models (since these physiological variables are only measured at two points, there is no need for linear mixed models). For these latter analyses, variables for relevant sociodemographic and clinical confounds will need to be included as change in anxiety is not assigned by randomization akin to group assignment. Comparisons between the groups of higher anxiety and low anxiety will be made using one-way analysis of variance to determine differences in vascular function, mSNA, and inflammation. Baseline values for the higher anxiety group will be compared to the values obtained from the low anxiety group during their one-time experimental visit.

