## Sample Size

Using the estimating equations of Diggle et al. (2002) and based on three assessments for primary and secondary outcomes and a correlation of outcome measures over the duration of the study within individuals of 0.4, a total of 38 participants are needed per group to detect an effect size of 0.5 SD with 80% power at an  $\alpha=0.05$  (as calculated in SAS 9.3 using relevant formula). Assuming an 10% dropout rate our sample size would need to be adjusted to  $38/(1-0.1)=43$  per group using the formula from Friedman et al. (2010). A 0.5 SD difference on the anxiety inventory should represent a clinically significant effect. A corresponding change of similar magnitude on the better studied Hamilton Depression Rating Scale (not used in this study) has been considered clinically significant (Hegerl et al. 2012). Similarly, we are powered to detect clinically significant effects for the secondary outcomes of vascular function. We will

assess large vessel measures (e.g. pulse wave velocity), resistance vessel measures (forearm blood flow), and microvascular measures in the retina. In a study of brachial artery flow-mediated dilation (FMD), a reduction in FMD of 0.66 SD was associated with a 30% increased risk of cardiovascular events (Shimbo D et al. 2007). Similar results were seen in another population-based study wherein each 0.66 standard deviation in FMD was associated with an 18% increased risk of composite cardiovascular events and 36% increase risk of myocardial infarction, resuscitated cardiac arrest or coronary heart disease death (Yeboah J et al. 2009). Thus, we should be powered to detect clinically significant changes in vascular function.

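### The sections disagree on how often the physiological outcomes are measured, and no visit lists a retinal measurement after ACT

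*Combined protocol and SAP*

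**What the plan says.** - **Purpose.** It states that "vascular function (via non-invasive, well-established techniques) will be performed at baseline and 12 weeks post-ACT group intervention session". It describes the 6-week contact as a repeat of the anxiety surveys only, and adds: "After 12 weeks, anxiety and vascular assessments will be repeated".
- **Research Question and Hypothesis, prediction 4.** "ACT will improve microvascular, including retinal vascular, and large elastic artery function".
- **Secondary Endpoint Analysis.** Vascular function, mSNA and inflammation "will be explored in analogous to the above", which points to the three-visit mixed model for the Beck Anxiety Inventory (BAI). Their association with change in anxiety is to be tested by linear regression, "since these physiological variables are only measured at two points, there is no need for linear mixed models".
- **Sample Size.** The calculation rests on "three assessments for primary and secondary outcomes". Power is also claimed for vascular function, naming PWV, "resistance vessel measures (forearm blood flow), and microvascular measures in the retina". The supporting effect size comes from flow-mediated dilation (FMD): "a reduction in FMD of 0.66 SD was associated with a 30% increased risk of cardiovascular events".
- **Assessment Schedule.** It itemises the tests at Visit 1, Visit 2, 6 weeks and Visit 4. Visit 4 is described as repeating Visit 2. Controls follow the same schedule apart from the workshop (Visit 3).

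**The concern.** No single number of time points satisfies all four places. Three consequences follow, all for secondary outcomes.

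1. **Retina.** Prediction 4 and the power statement both rely on a retinal outcome, but the only listed retinal tests come before ACT. Study staff working from the Visit 4 list would not collect the follow-up value, and it could not be recovered at analysis.
2. **Association analysis.** The reason given for avoiding mixed models does not hold for mSNA and forearm blood flow, the outcomes of predictions 2 and 3.
3. **Power.** The three-assessment calculation is offered in support of outcomes, such as PWV, that are measured only at baseline and 12 weeks.

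**Working it through.** **Time points listed in the Assessment Schedule**

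| Outcome | Visit 1 | Visit 2 | 6 weeks | Visit 4 | Count |
|---|---|---|---|---|---|
| mSNA | – | yes | yes | yes | 3 |
| Forearm blood flow (VOP) | – | yes | yes | yes | 3 |
| PWV, carotid compliance | – | yes | – | yes | 2 |
| 24-hour blood pressure | – | yes | – | yes | 2 |
| Blood and endothelial markers | – | yes | – | yes | 2 |
| Retinal imaging | yes | – | – | – | 1 |

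The E4 wristbands that record heart rate variability (part of prediction 5) are also worn at Visit 2, 6 weeks and Visit 4, as well as during retinal imaging at Visit 1. The 6-week vascular visit is not a stray line: its procedures are itemised, and the compensation schedule pays separately for a visit of about 2 hours.

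The retinal tests stand under Visit 1. Because Visit 4 repeats Visit 2, and neither list contains a retinal test, that instruction does not bring them back. The count after ACT is zero, so on the listed schedule an ACT effect on the retina cannot be estimated at any sample size.

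**Inputs from Sample Size:** effect 0.5 SD, power 80%, α = 0.05, within-person correlation ρ = 0.4, dropout 10%. Sidedness is not stated; a two-sided test reproduces the plan (one-sided gives 30). So z = 1.9600 + 0.8416 = 2.8016, and 2z² = 15.698.

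**Reproducing the plan.** n per group = 2z²[1 + (m − 1)ρ]/(m d²).
- m = 3: 15.698 × 1.8/(3 × 0.25) = 37.67, so 38; 38/0.9 = 42.2, so 43. Both match.

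**Changing only the number of assessments.**
- m = 2: 15.698 × 1.4/(2 × 0.25) = 43.95, so 44; 44/0.9 = 48.9, so 49.
- Power at 38 per group: 0.5/√(0.7 × 2/38) = 2.605; Φ(2.605 − 1.960) = 0.74.

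**Baseline-adjusted comparison.** The formula above counts baseline as one of the assessments. With k follow-up visits and adjustment for baseline, the variance factor is V = [1 + (k − 1)ρ]/k − ρ², and n = 2z²V/d².
- k = 1 (12 weeks only): V = 1 − 0.16 = 0.84; n = 52.7, so 53; 53/0.9 = 58.9, so 59.
- k = 2 (6 and 12 weeks, equal effect at both): V = 0.70 − 0.16 = 0.54; n = 33.9, so 34.

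The like-for-like contrasts are therefore 44 against 38 on the plan's formula, and 53 against 34 when baseline-adjusted.

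**Baseline-adjusted power with one follow-up (V = 0.84).** If all 150 are randomised 2:1 and 10% are lost, 135 remain, or 90:45.

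| Effect | 38:38 | 90:45 |
|---|---|---|
| 0.5 SD | 0.5/√(0.84 × 2/38) = 2.378; 66% | 0.5/√(0.84 × (1/90 + 1/45)) = 2.988; 85% |
| 0.66 SD | 3.139; 88% | 3.944; 98% |

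On the plan's formula with m = 2, power at 90:45 and 0.5 SD is 90.5%.

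**The case against.** **Retina.** The visit lists are visibly incomplete: baroreflex sensitivity is described under Experimental Methods but itemised at no visit. The Purpose section says vascular assessments are repeated after 12 weeks, and Experimental Methods does not confine the retinal tests to Visit 1. This stands. A reader might infer that the retinal follow-up was abandoned or never planned; the documents do not show that. They show only that no visit lists it.

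**Power.** Setting 53 against the plan's 38 would change the formula as well as the number of assessments, so that gap should not be read as the cost of the conflict. The 38:38 split is not the planned allocation, since Randomization specifies 2:1. Sample Size ties 0.5 SD to the anxiety inventory and supports the vascular claim with 0.66 SD. The State-Trait Anxiety Inventory is also a secondary outcome and is measured three times, so the three-assessment wording is right for some secondary outcomes. All of this stands. A reader might infer that the trial is underpowered for vascular outcomes; the figures do not support that at planned enrolment.

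One caution remains: the method matters. A change-score comparison with one follow-up has V = 2(1 − 0.4) = 1.2. At 90:45 that gives 70.5% at 0.5 SD (0.5/0.2 = 2.5) and 91% at 0.66 SD (0.66/0.2 = 3.3).

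**Association analysis.** Regressing 12-week physiological change on 12-week anxiety change remains valid when a 6-week value exists but is unused. A reader might infer that a mixed model is required, but the loss is precision only. Its size depends on correlations that the documents do not give. The group comparison, planned along the lines of the primary model, can already use week 6.

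**Conclusion.** The conflict is real and lies in the current text. Its most consequential part is the retina: a stated prediction and a power statement have no listed measurement after ACT. The two-point premise is false for mSNA and forearm blood flow. The three-assessment basis does not apply to PWV or to the other outcomes measured only at baseline and 12 weeks. For these, the plan's formula needs 44 per group (49 with dropout), and 38 per group gives 74% power.

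The basis is misstated, but a shortage is not shown: baseline-adjusted power at 90:45 is 85% at 0.5 SD and 98% at 0.66 SD. These figures assume a two-sided test, equal correlation of 0.4 between visits, and all 150 randomised 2:1 with 10% loss. The BAI is scheduled at all three time points its model uses, so the primary outcome is unaffected. The point should be fixed, chiefly for the retina; the power and regression parts are smaller corrections.

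**What to change.** 1. **Retina.** Reconcile Purpose, prediction 4, the Visit 1, 6-week and Visit 4 lists, and Sample Size. If a repeat was intended, list the retinal tests at Visit 4. If not, drop the retinal ACT prediction and power statement, and limit the retina to a baseline description or comparison.
2. **Time points.** Correct the two-point statement in Secondary Endpoint Analysis, align Purpose with the 6-week vascular visit, and state once, for each outcome, which visits each analysis uses. Heart rate variability should be included. Bringing the 6-week mSNA and forearm blood flow values into the association analysis through a mixed model is optional. If this is done, state the assumption of a common slope across visits.
3. **Power.** Limit the three-assessment basis to outcomes measured three times. For those measured only at baseline and 12 weeks, restate power at the planned 2:1 allocation and name the method.

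The cost is text and restated figures, plus one mixed model for two outcomes if that option is taken. Adding retinal tests may lengthen Visit 4, which the compensation schedule puts at about 4 hours, the same as Visit 2.

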- Abnormal resting 12-lead ECG (e.g., evidence of myocardial infarction, left ventricular hypertrophy, left-bundle branch block, 2nd or 3rd degree AV block, atrial fibrillation/flutter, atherosclerosis).
- Serious neurologic disorders including seizures.
- History of renal failure, dialysis or kidney transplant.
- Use of any investigational products or investigational medical devices within 30 days prior to screening, or requirement for any investigational agent prior to completion of all scheduled study assessments.
- Recent flu-like symptoms within the past 2 weeks.
- Pregnant or breastfeeding at screening, or planning to become pregnant (self or partner) at any time during the study. A urinary pregnancy test will be done on all females. If test is positive, the subject will be excluded.
- History of rheumatoid arthritis, Grave's disease, systemic lupus erythamatosi, and Wegener's granulomatosis.
- Taking anticoagulation, anti-seizure, or antipsychotic agents.
- Start of or dose change to an antidepressant or anti-anxiety medication within the past 3 months (if no change in medication or dose in past 3 month, then subject will be eligible).
- Intention to start or current psychotherapy for anxiety and/or depression while enrolled in study.
- Immunodeficiency or systemic autoimmune disease.
- History of bleeding disorders or conditions of the microcirculation (i.e. von Willebrand disease, Raynaud's disease).
- History of co-morbid condition that would limit life expectancy to <1 year.
- Taking chronic non-steroidal anti-inflammatory drugs (NSAIDs) such as aspirin, indomethacin, naproxen, acetaminophen (Tylenol®), ibuprofen (Advil®, Motrin®) and not able or willing to go off of for 2 weeks prior to each study visit.
- Taking cox-2 inhibitors (Celebrex®, Vioxx®, etc) or allopurinol (Zyloprim®, Lopurin®, Aloprim®).
- Taking steroids or biologics: corticosteroids (prednisone); methotrexate, infliximib (Remicade®), etanercept (Enbrel®); anakinra (Kineret®).
- Those who are currently donating blood, platelets, or plasma at the time of screening.
- Vulnerable populations (prisoners, etc.) will not be eligible to participate in this study.
- Current alcohol abuse.
- On weight loss drugs (i.e. orlistat (Xenical®), sibutramine (Meridia®), phenylpropanolamine (Acutrim®)), or similar over-the-counter medications within 3 months of screening.
- Any condition that, in the view of the PI or Co-I, places the subject at high risk or poor treatment and study compliance.

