## Assessment Schedule

### Intervention Group

- 1) Visit 1: Consent and Screening
  - a) Explanation of the study; reading and signing of written informed consent document
  - b) If subject consents, but requires a 2 week washout for vitamins or supplements, aspirin, NSAIDs, PDE-5 or PDE-3 inhibitors, Visit 2 will not be scheduled for 2 weeks post-Visit 1 completion.
  - c) If subject consents and no washout is needed, screening tests will be performed on the same day to determine further eligibility by the following:
    - i) Research staff will obtain resting vitals (heart rate, blood pressure) and resting 12 lead ECG.
    - ii) -Subject will fill out the Demographics Document, Health History Survey (including current medications), Sleep Surveys (including the Berlin Questionnaire, Karolinska Sleep log and the Sleep Quality Assessment [PSQI]) and Modified Activity Questionnaire. The following questionnaires will be completed online: State-Trait Anxiety Inventory, Positive and Negative Affect Schedule-Expanded Form, Anxiety Inventory, Depression Inventory, Early Experience Questionnaire, Acceptance and Action Questionnaire II, Committed Action Questionnaire, Short Form Health Survey.
    - iii) -Research nurse or trained staff will obtain venous blood draw (1/2 teaspoon) using butterfly needle for UIHC pathology labs: TSH only.
  - d) Subject will meet with a physician or other trained interviewer who will ask detailed questions about their medical history, structured psychiatric history (MINI) and

medication use. The subject may skip or refuse to discuss any questions/topics they wish not to answer. To minimize participant burden and accommodate participant schedules, visit procedures may be split across multiple days.

- e) Subject will undergo visual acuity, intraocular pressure test as well as a blood pressure measurement. The subject will then undergo ocular coherence tomography and laser-speckle blood flow imaging. As with microneurography (Visit 2), two E4 wristbands (one on each wrist) will be worn and a mental math test and a cold pressor test may also be performed during laser-speckle blood flow imaging.
- 2) Visit 2: Pre-Intervention Visit
- a) Subject will arrive at the CRU between 7-9 am after an overnight 8 hour fast (water encouraged).
    - i) Subjects on vasoactive medications will be asked to hold medications on the morning of experimental testing, but will bring medications with them to be taken after the visit.

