  - b) CRU staff/nurse will obtain urine or serum sample for pregnancy test (women of childbearing age only).
  - c) Prior to experimental testing, the subject will complete (for a 2nd time) the following surveys/questionnaires: State-Trait Anxiety Inventory; Positive and Negative Affect Schedule-Expanded Form; Anxiety Inventory; Depression Inventory; Early Experience Questionnaire; Acceptance and Action Questionnaire II; Committed Action Questionnaire; Short Form Health Survey; Sleep Surveys (including the Berlin Questionnaire, Karolinska Sleep log and the Sleep Quality Assessment [PSQI])
  - d) A research staff member trained in microneurography will record from the peroneal nerve with a microelectrode for measurement of muscle sympathetic nerve activity (See 'Methods' for details). Subject will be given an mSNA Questionnaire to assess any follow-up discomfort at the sight of microneurography electrode over the next 7 days and mail it back to the study staff in 7 days. Participants will wear two E4 wristbands (one on each wrist) during the procedure. Measures of brachial artery blood flow using Doppler ultrasound, a mental math test, and a cold pressor test may also be performed during microneurography.
  - e) Primary Endothelial Cell Protein Collection and blood sample: Subject will lie supine and a CRU nurse or physician will insert venous 18 G or 20 G catheter into antecubital vein.
    - [name], nurse or physician will perform J wire endothelial cell collection (3 wires) through the 18 G IV catheter (see 'Experimental Methods' for details).
  - f) After 15-20 minutes, CRU nurse will obtain blood samples through catheter:
    - 1 light green PST tube (4.5 mL) for lipid panel, insulin, glucose, hs-CRP; sent to UIDL
    - 1 dark green Na+Hep tube (10 mL) for catecholamines; sent to UIDL on ice
    - Extra blood collected for specialized labs performed in Co-I's lab:
      - (1) 1 light green PST tube (4.5 mL each) for [name] Research lab; extra plasma
      - (2) 1 lavender EDTA tube (4 mL) for [name] Research lab
      - (3) 4 red top tubes (5 mL each) for [name] Research lab; to test interleukin-6, tumor necrosis factor-alpha, and oxidative stress proteins)
  - g) Venous Occlusion Plethysmography (VOP) will be performed (see 'Experimental Methods' for details).

- h) Pulse Wave Velocity (PWV) and Carotid Compliance (CC) (see 'Experimental Methods' for details). Pulse wave velocity will be performed two times.

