      - (1) Subjects on vasoactive medications will be asked to hold medications on the morning of experimental testing, but will bring medications with them to be taken after the visit.
    - ii) A research staff member will administer Sleep Surveys (including the Berlin Questionnaire, Karolinska Sleep log and the Sleep Quality Assessment [PSQI])
    - iii) A research staff member trained in microneurography will record from the peroneal nerve with a microelectrode for measurement of muscle sympathetic nerve activity (See 'Methods' for details). Subject will be given an mSNA Questionnaire to assess any follow-up discomfort at the sight of microneurography electrode over the next 7 days and mail it back to the study staff in 7 days. Participants will wear two E4

- wristbands (one on each wrist) during the procedure. Measures of brachial artery blood flow using Doppler ultrasound, a mental math test, and a cold pressor test may also be performed during microneurography
- iv) Venous Occlusion Plethysmography (VOP) will be performed (see 'Experimental Methods' for details).
  - v) Subject will receive snack or meal from CRU dining room.
- 5) Visit 4: 2nd Experimental Visit (12-weeks post-intervention)  
All experimental procedures described in Visit 2 will be repeated.
- a) Subject will arrive at the CRU between 7-9 am after an overnight 8 hour fast (water encouraged).
    - i) Subjects on vasoactive medications will be asked to hold medications on the morning of experimental testing, but will bring medications with them to be taken after the visit.
  - b) CRU staff/nurse will obtain urine or serum sample for pregnancy test (women of childbearing age only).
  - c) Prior to experimental testing, the subject will complete (for a 2nd time) the following surveys/questionnaires:
    - i) State-Trait Anxiety Inventory
    - ii) Positive and Negative Affect Schedule-Expanded Form
    - iii) Anxiety Inventory
    - iv) Depression Inventory
    - v) Early Experience Questionnaire
    - vi) Acceptance and Action Questionnaire II
    - vii) Committed Action Questionnaire
    - viii) Short Form Health Survey
    - ix) Sleep Surveys (including the Berlin Questionnaire, Karolinska Sleep log and the Sleep Quality Assessment [PSQI])

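### No listed procedure measures height or weight, so BMI may be unavailable for the required confounder adjustment, and the higher- versus low-anxiety ANOVA has no covariates

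*Combined protocol and SAP*

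**What the plan says.** The protocol's Secondary Endpoint Analysis section sets out two non-randomised analyses of physiology.

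- **Regressions on change in anxiety.** These are fitted across the randomised groups. The plan accepts that they are observational: "variables for relevant sociodemographic and clinical confounds will need to be included as change in anxiety is not assigned by randomization". No confounder is named. The outcomes are those in "The novel physiological variables (vascular function, mSNA, inflammation) will serve as secondary outcomes".
- **Higher versus low anxiety at baseline.** "Comparisons between the groups of higher anxiety and low anxiety will be made using one-way analysis of variance". No covariate is mentioned. This analysis addresses prediction 1 under Research Question and Hypothesis. The low-anxiety group attends once, and the Assessment Schedule has no entry for that visit.

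On measurement, the Visit 1 entry reads "Research staff will obtain resting vitals (heart rate, blood pressure) and resting 12 lead ECG". Visit 1 also has forms: "Subject will fill out the Demographics Document, Health History Survey (including current medications), Sleep Surveys (including the Berlin Questionnaire, Karolinska Sleep log". Visit 2 adds blood tests, including "1 light green PST tube (4.5 mL) for lipid panel, insulin, glucose, hs-CRP; sent to UIDL", and the vascular, nerve and 24-hour blood pressure studies. For Visit 4, "All experimental procedures described in Visit 2 will be repeated". Controls follow the same schedule without the workshop.

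**The concern.** Adiposity is an obvious candidate confounder for hs-CRP, IL-6, sympathetic nerve activity and arterial stiffness. That is a subject-matter judgement; the plan does not say it. If people with higher anxiety also differ in BMI, an unadjusted difference between the higher- and low-anxiety groups mixes the two. If weight moves together with anxiety over 12 weeks for reasons other than the anxiety itself, the slope on anxiety change partly measures weight change.

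The plan commits to adjusting the regressions, but nothing in its schedule shows where a body-size variable would come from. A weight that nobody recorded at a past visit cannot be recovered at analysis. The ANOVA has a second problem: as written it would leave BMI out even if BMI had been collected.

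**Working it through.** **1. Is body size measured anywhere?**

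| Place in the protocol | What is listed | Height, weight, waist or BMI |
|---|---|---|
| Inclusion and Exclusion Criteria | age, blood tests, ECG, medical history, drugs | no limit set |
| Visit 1 | heart rate, blood pressure, ECG, forms, TSH, interview, eye tests | not listed |
| Visit 2 | surveys, nerve recording, cell collection, bloods, VOP, PWV, carotid compliance, 24-hour monitor | not listed |
| 6-week visit | surveys, nerve recording, VOP | not listed |
| Visit 4 | repeat of Visit 2 | not listed |
| Experimental Methods, items 1 to 9 | assay and device methods | not listed |
| Low-anxiety visit | no procedure list | unknown |

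Lipids, insulin and glucose are drawn at Visits 2 and 4, but they do not measure adiposity. The activity questionnaire is listed at Visit 1 only.

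**2. Could a form fill the gap?** The items of the demographics, health-history and sleep forms are not reproduced. The sleep surveys, including the Berlin Questionnaire, are given again at Visit 2, the 6-week visit and Visit 4. If one of these forms asks for weight, a self-reported baseline and even a self-reported change could exist. The documents neither show this nor exclude it.

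**3. Does the sample size depend on this?** The plan's figure reproduces: n per group = 2(1.960 + 0.842)² × [1 + (3 − 1) × 0.4] / (3 × 0.5²) = 37.67, rounded up to 38. Then 38/0.9 = 42.2, rounded up to 43. No covariate enters the formula, so the sample size is untouched.

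**4. Size of a possible bias in the regressions.** Inputs from the documents: 150 enrolled (Description of Study Population) and 10% dropout (Sample Size), so 150 × 0.9 = 135 completers. The correlations are assumptions. Let r be the correlation of weight change with anxiety change, and b the standardised slope of the outcome on weight change. Suppose anxiety change has no effect of its own and weight change is a confounder, not a mediator. Then:

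- spurious slope = r × b
- standard error ≈ 1/√132 = 0.087
- z = slope / 0.087
- false-positive rate = P(|N(z, 1)| > 1.96)

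| r | b | Spurious slope (SD per SD) | z | False-positive rate | Simulated rate |
|---|---|---|---|---|---|
| 0.1 | 0.2 | 0.02 | 0.23 | 5.6% | 5.7% |
| 0.2 | 0.3 | 0.06 | 0.69 | 10.6% | 10.4% |
| 0.3 | 0.3 | 0.09 | 1.03 | 17.9% | 17.5% |
| 0.3 | 0.4 | 0.12 | 1.38 | 28.1% | 28.0% |

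The last column is from 20,000 simulated data sets of 135.

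**5. The higher- versus low-anxiety comparison.** The same product rule applies to baseline BMI. Correlations of 0.1 to 0.3 with the anxiety variable and 0.2 to 0.5 with the outcome would turn a true partial correlation of zero into 0.02 (0.1 × 0.2) to 0.15 (0.3 × 0.5). No false-positive rate is given here, because the size of the low-anxiety group is not stated.

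**The case against.** **The visit lists are not a complete inventory.** Eligibility needs creatinine, ALT and AST, yet the Visit 1 blood draw is for TSH only and no later visit lists those tests. The continuous finger blood pressure recording for baroreflex sensitivity is not a separate step at any visit. Silence about a scale is therefore weak evidence that nobody is weighed. This stands. A reader might infer that adiposity cannot be adjusted for at all, or that weight change to 12 weeks is bound to be unknown. The documents do not support either, because the form items are not shown and the sleep surveys are repeated.

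**The sponsor has not named weight as a confounder.** A reader might take the exclusion that begins "On weight loss drugs" as a sign that the sponsor sees weight change as a threat. It is one of many medication exclusions and carries no reason. It does show that there is no direct limit on body size.

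**Weight change may be a mediator.** It is measured over the same 12 weeks as anxiety change. If less anxiety alters weight, and weight alters physiology, conditioning on it removes part of the hypothesised effect. This stands, and it rules out making weight change a compulsory covariate.

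**Stable adiposity largely cancels when outcomes are analysed as changes.** Also true, so baseline BMI does less in the change regressions than in the cross-sectional comparison. There the objection has no force: nothing cancels, and the model has no covariates.

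**The affected analyses are secondary and exploratory.** Correct, and this limits the weight of the point. Even so, the cross-sectional comparison is the planned test of prediction 1.

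**Conclusion.** The point holds in a limited form. No listed procedure measures height or weight, no confounder list is given, and the low-anxiety visit is undescribed. Unless a form supplies the data, BMI and weight change will be unavailable for an adjustment that the plan itself requires. The firmest part is the one-way ANOVA, which as written adjusts a non-randomised comparison for nothing.

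The size is uncertain. For weight change, the assumed correlations give anything from a negligible effect (about 6% false positives) to a serious one (about 28%), and the documents do not show which end applies. That range also assumes that weight change confounds and does not mediate. The primary BAI analysis, the validity of the randomised ACT-versus-control comparison and the sample size are unaffected. This is a cheap improvement to secondary analyses and does not threaten the trial's main result.

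**What to change.** 1. **Measurement.** Record measured height once, and weight at Visits 2 and 4 and at the low-anxiety visit. Alternatively, name the form that already supplies them and the visits at which it is completed. List the low-anxiety visit's procedures in the Assessment Schedule.
2. **Higher versus low anxiety.** In Secondary Endpoint Analysis, replace the one-way ANOVA with an ANCOVA that includes baseline BMI, age and sex.
3. **Regressions on anxiety change.** Pre-specify the confounder list and include baseline BMI in it. Show results with and without weight change as a sensitivity analysis only, and state that weight change may lie on the pathway from anxiety to physiology.

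The cost is a few minutes per visit, mostly at visits already scheduled, plus a few form fields and a few lines of analysis text. Participants already past Visit 2 will lack a measured baseline weight. If a form holds a self-reported value it could be used for them, flagged as such; otherwise they drop out of the BMI-adjusted models, and their number should be reported.
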